## 2.2 RATIONALE

This study aims to evaluate the antimalarial activity of co-administered single doses of OZ439 and PQP in the IBSM model, and enable characterisation of the exposure-response relationship between OZ439 and PQP PK and blood stage asexual parasitaemia. Previous research has shown that the IBSM model is a good predictive model for real world antimalarial drug activity with single drug administration [7]. However, it is yet to be determined if the model is an effective predictive tool when two or more drugs are administered in combination.

We hypothesise that data obtained in a controlled disease-like setting (Phase 1 drug combination IBSM model) can be used to effectively predict the outcome of Phase 2 studies in patients with uncomplicated malaria. To evaluate this hypothesis, we will assess if the outcome of this trial can be used to predict what was observed in patients with uncomplicated malaria in the MMV\_OZ439\_13\_003 Phase 2b combination trial [8].

The doses chosen for use in Cohort 1 are based on the PK/PD relationships from the IBSM monotherapy studies and potential PD interaction effects of the combination based on the phase IIb study. Several doses will be tested in Cohort 1, which should achieve parasite reduction but not complete cure, such that parasite regrowth can be observed, allowing an initial estimation of the PK/PD parameters of the 2 drugs when combined. The results of the first cohort will then be used to guide dose selection for Cohort 2 and maximising the information on the PD interaction effect.

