9.1 OVERVIEW

A population PKPD model will be derived from the concentrations and parasitaemia observed in the challenge volunteers. It is achieved by sequentially developing a population PK model to describe the observed individual PK profiles and a population PD model for quantifying the relationship of plasma concentrations and the parasite clearance. The model building is supported by PK/PD data from studies QP12C10 and QP13C05 for OZ439 and PQP mono treatment in healthy volunteers.

The final model will be employed to simulate patients of the OZ439 mono study 12_006 and the OZ439/PQP combo study 13_003. Predictions of the ACPR28 will be used to evaluate the predictive power of the human challenge model by comparing the simulations with the observed ACPR28 in clinical trials 12_006 and 13_003.

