Model evaluation

Assessment of model adequacy and decisions about increasing model complexity will be driven by the data and guided by goodness-of-fit criteria, including

1. visual inspection of diagnostic scatter plots (observed vs. predicted concentration, residual/weighted residual vs. predicted concentration or time and histograms of individual random effects, for example),
2. successful convergence of the minimization routine with at least 2 significant digits in parameter estimates,
3. plausibility of parameter estimates,
4. precision of parameter estimates,
5. correlation between model parameter estimation errors < 0.95, and
6. the Bayesian information criterion, given the minimum objective function value and number of estimated parameters.

For the nonlinear fixed effects models, additional diagnostic plots will be produced:

7. objective function values across multiple fits from randomised initial guesses, and

	
STATISTICAL ANALYSIS PLAN
	
QP17C19

		
Page 40 of 53

8. profile likelihood plots

All parameter estimates will be reported with a measure of estimation uncertainty, such as the standard error of the estimates. The individual PK fits will be used to evaluate the adequacy to use the individual PK parameter estimates as regression parameters for PD modelling.

The adequacy of simulation with the final models will be evaluated by visual predictive checks. Visual predictive checks for each dose level will be performed by simulation of the study 200 times taking parameter estimation uncertainty into account. 95%-confidence intervals for the 5th percentile, the median, and the 95th percentile will be derived and compared to the corresponding values based on the data.

To compare simulations of the final model with patient data, both, the data and the simulation will be transformed into a life table format indicating for each individual the time of recrudescence, i.e., the time at which parasite levels re-occur after being BLQ or the time for which parasitaemia levels are minimum, or, if not defined, the last observed time point without recrudescence. The Kaplan-Meier estimator [KAP58, THE15, TER00] will be used to compare model and data.

PK modelling

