The mutual model assumes that $\alpha_{12} = \alpha = \alpha_{21}$ and $\beta_{12} = \beta = \beta_{21}$. Thereby, the number of interaction parameters is reduced from 4 to 2 in the mutual model.

IIV will be assumed on all parameters except the Hill coefficient and the interaction parameters. Parameters are assumed to be log-normally distributed besides the log-transformed parasite baseline value for which the normal distribution was assumed. The standard deviation of the IIV will be fixed to 0.2 for the SysFit approach. When parameters are estimated with Monolix, standard deviations of the IIV will be estimated.

Using the SysFit approach for PD modelling, parameter estimation will be started from 24 initial guesses. Identifiability of the best fit will be analysed using the profile likelihood method. In case, several local optima with similar objective value are found, those local optima will be investigated and it will be checked using modelling, if additional cohorts could help to reduce the number of local optima.

Using Monolix, optimization will be initialized with the estimated values obtained with SysFit. If optimization with Monolix poorly converges for some of the parameters as being assessed by the Monolix convergence traces, these values will be fixed to the value obtained with SysFit.

Simulations to predict ACPR28 in patients

Simulations of patients will build on the patient characteristics found in the 12_006 and 13_003 studies. Simulations will be performed as if patient PK and PD information was completely missing. Only covariates such as weight, actual dose, expected exposure and parasitaemia levels at $t = 0$ (shortly before treatment) will be used.

	
STATISTICAL ANALYSIS PLAN
	
QP17C19

		
Page 43 of 53

For each dose group, n = 200 patients will be randomly drawn with replacement. Individual parameters will be sampled from the IIV estimated by Monolix, taking covariates of the randomly chosen patients into account.

Individuals in each dose group will be simulated at densely sampled time points between 0 and 1600 hours. Initial values for the parasitaemia simulation will be fixed to the parasitaemia level of the selected patient.

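### The ACPR28 prediction for the Phase 2 arms carries no parameter uncertainty, and how agreement with the observed result will be judged is not stated

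*SAP*

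**What the plan says.** Protocol 2.2 puts forward the hypothesis that combination data from the challenge model "can be used to effectively predict the outcome of Phase 2 studies in patients with uncomplicated malaria", and names the Phase 2b combination trial 13_003 as the test case. SAP 9.1 turns this into an analysis and adds the OZ439 monotherapy study 12_006: "Predictions of the ACPR28 will be used to evaluate the predictive power of the human challenge model by comparing the simulations with the observed ACPR28". SAP 2.3 lists model-predicted ACPR28 under the primary endpoints.

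The simulation is described in SAP 9.4, under the heading on predicting ACPR28 in patients: "For each dose group, n = 200 patients will be randomly drawn with replacement", and then "Individual parameters will be sampled from the IIV estimated by Monolix, taking covariates of the randomly chosen patients into account". That text mentions neither repeated simulated trials nor a draw of the population parameters from their uncertainty.

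Earlier in 9.4, under model evaluation, the visual predictive checks are done differently: "by simulation of the study 200 times taking parameter estimation uncertainty into account", with 95% confidence intervals for the simulated percentiles. For patient data, the same subsection says only that Kaplan-Meier estimates will be used to set model against data. Neither document gives an interval, margin or other criterion for the ACPR28 comparison.

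**The concern.** The comparison with 12_006 and 13_003 is how the SAP evaluates predictive power. A predicted ACPR28 has two layers of uncertainty: variation between patients, and imprecision in the population values themselves. The plan samples the first and is silent on the second.

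Without the second layer there is no prediction interval. A gap of about 10 points between simulated and observed ACPR28 might lie within the model's own imprecision, and a close match might be luck. The Phase 2b outcome was already known when the study was planned (Protocol 2.1 reports that no arm reached the 95% threshold). With no stated way of judging agreement, the standard could be settled after the predictions are seen.

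**Working it through.** There is no stated figure to reproduce: the 200 is given without justification, and no margin or error rate is attached to the comparison.

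**1. What varies in each simulation (SAP 9.4).**
- Visual predictive checks: 200 replicates of the study, with parameter estimation uncertainty included.
- Patient prediction: 200 resampled patients per dose group, their covariates, and IIV around the population estimates. Nothing else is mentioned.

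**2. Where the uncertainty of each parameter goes.**
- Typical Emax, EC50 and Hill: taken from the monotherapy PD models and fixed in the combination model (9.4, model-building step 5). The IIV of Emax and EC50 is fixed in the same way. Their imprecision is dropped before the patient simulation begins.
- Interaction parameters: estimated from this study, but with no IIV assumed on them (9.4, PD modelling). Under IIV-only sampling they enter as constants.
- Hill coefficients: both fixed and without IIV.
- Any parameter that converges poorly in Monolix: fixed at its SysFit value.

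**3. Monte Carlo error of one run of 200.** 95% half-width = 1.96 × √(p(1−p)/200).
- p = 0.70: 1.96 × 0.0324 = 6.4 points
- p = 0.80: 1.96 × 0.0283 = 5.5 points
- p = 0.95: 1.96 × 0.0154 = 3.0 points

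The observed arm has sampling error too. Its size m is not in the documents. For simulated minus observed, 1.96 × √(p(1−p)(1/200 + 1/m)) at p = 0.70 gives 14.2 points for an assumed m = 50, 11.0 for m = 100 and 9.0 for m = 200.

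**4. Parameter uncertainty (illustration only).** The documents give no standard errors, so the real effect cannot be calculated. Suppose a patient is cured when an individual log-scale margin exceeds zero, and let r be the SE of the typical margin divided by the between-patient SD. A predicted proportion p then has the 95% range Φ(z ± 1.96r), with z = Φ⁻¹(p). For p = 0.80, z = 0.842.
- r = 0.2: Φ(0.842 − 0.392) = Φ(0.450) = 67%; Φ(1.234) = 89%
- r = 0.4: Φ(0.842 − 0.784) = Φ(0.058) = 52%; Φ(1.626) = 95%

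Here r stands for the combined imprecision of the predicted effect. It cannot be tied to a single parameter, and the interaction parameters have no between-patient SD to scale by.

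**5. Cross-check by simulation.** The same model was run at a predicted 70%, with 200 patients per run and an assumed IIV SD of 0.5.

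| Assumed SE | r | 95% range |
|---|---|---|
| none (IIV only) | 0 | about 63.5-76% |
| 0.05 | 0.1 | 60.5-79% |
| 0.1 | 0.2 | 54-83.5% |
| 0.2 | 0.4 | 38.5-91% |

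The widening is modest if r is near 0.1 and large if r is 0.2 or more. The documents do not show which applies.

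**The case against.** The strongest reply is that the SAP is silent on this step and does not exclude the uncertainty, and that Protocol 10.3.2 leaves modelling detail to a modelling analysis plan that is not among the documents. The first part is fair: a single simulation without parameter uncertainty is the plain reading, not an explicit statement. The second part does not settle the point. SAP 1.1 says the SAP covers the PKPD modelling and supersedes the protocol where they differ, and SAP section 9 does not defer to another plan.

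Second, uncertainty is not hidden altogether. SAP 9.4 requires every estimate to be reported with a measure of uncertainty and provides profile-likelihood intervals for the SysFit parameters, and 9.6 requires the limitations of the prediction to be discussed. That stands, but none of it yields an interval for ACPR28.

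Third, the output is more than one number per arm. There are Kaplan-Meier curves by dose group, simulated to 1600 hours, for two trials. Dose ordering, curve shape and gross mismatch can all be informative. That stands too, so a reader who infers that the comparison cannot be interpreted at all goes too far.

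Fourth, a reader might infer that this comparison is why the study was run. The formal primary objectives are the PK/PD relationship and safety. The prediction is a hypothesis in the protocol's rationale, although SAP 2.3 places predicted ACPR28 under the primary endpoints.

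**Conclusion.** The point holds as an analysis choice that should be changed. As written, the predicted ACPR28 has no prediction interval, leaves out uncertainty in the interaction parameters and in the fixed monotherapy values, and is compared with the observed result without a stated way of judging agreement. This is more than missing detail, because the SAP already applies uncertainty propagation to its visual predictive checks.

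Only the Monte Carlo part of the size, 3.0 to 6.4 points between 95% and 70%, follows from the plan itself, and it is minor. The ranges of 67-89% and 52-95% rest on assumed ratios of 0.2 and 0.4. It is tempting to set the ratio at 1/√24 ≈ 0.20 from the 24 volunteers and call it a best case, but the documents do not support that: typical Emax, EC50 and Hill come from monotherapy studies whose sizes are not given, and the interaction parameters have no IIV.

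**What to change.** In SAP 9.4, for each Phase 2 arm:

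- Simulate many replicate trials (for example 1,000) at the observed arm size.
- In each replicate, first draw the population parameters from their estimation uncertainty. Include the monotherapy Emax, EC50 and Hill values held fixed in the combination model, using the uncertainty from the monotherapy fits, and any values fixed at SysFit estimates, for example from profile likelihood. Copying the visual-predictive-check procedure would not be enough if it draws only what was estimated in the combination fit, because the intervals would then be too narrow.
- Then draw individual parameters from the IIV.
- Report the median and prediction interval of ACPR28 beside the observed value, and show the interval on the planned Kaplan-Meier figures (14.2.3.6 and 14.2.3.7).
- State before the simulations are run how agreement will be judged, and report the interval width. The criterion is the sponsor's choice. A rule that only asks whether the observed value falls inside the interval rewards imprecision, so width has to be part of the reading.

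The cost is SAP wording and computing time, and predictions that look less precise. Trial conduct does not change.

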9.5 ANALYSIS SOFTWARE AND WORKING DIRECTORY

All data processing, analysis, model setup and modelling result analysis including goodness-of-fit plots will be performed in R 3.5.1 using the IQRtools package 1.0.0 [IQR18].

NLME modelling will be performed with Monolix 2018R2 [MLX18] using Stochastic Approximation Expectation Maximization (SAEM) for parameter estimation. For PD modelling where typically the variance of random-effects cannot be estimated from the data, the IQRtools SysFit approach [KAS16] will be used to estimate typical and individual PD parameters.

A library of functions related to the analysis of PKPD studies of antimalarials may be used (available at <https://github.com/IntiQuan/iqrmalaria>).

APPENDIX 1: PLANNED LISTINGS

The following listings are planned to be generated for the QP17C19 study (note: Numbering is indicative only and may be updated based on CSR requirements):

	Listing Number	Listing Title	Population
16.2.1 Subject Disposition			
	Listing16.2.1.1	Study Enrolment and Completion/Discontinuation	All Enrolled
	Listing16.2.1.2	Visit Dates	All Enrolled
	Listing 16.2.1.3	Dose Group Assignment	All Enrolled
16.2.2 Protocol Deviations			
	Listing16.2.2.1	Protocol Deviations	All Enrolled
16.2.3 Subject Excluded from Analyses			
	Listing16.2.3.1	Analysis Population Assignment	All Enrolled
	Listing16.2.3.2	Subjects Excluded from Any Analysis Set(s)	All Enrolled
16.2.4 Demographic and Other Baseline Data			
	Listing16.2.4.1	Demography	All Enrolled
	Listing16.2.4.2	Inclusion and Exclusion Criteria	All subjects
	Listing16.2.4.3	Medical History	All Enrolled
	Listing16.2.4.4	Pregnancy Test	All Enrolled
	Listing16.2.4.5	Follicle Stimulating Hormone (FSH) Test	All Enrolled
	Listing16.2.4.6	RBC Alloantibody	All Enrolled
	Listing16.2.4.7	Serology and Special Tests	All Enrolled
	Listing16.2.4.8	Urine Drug Screen and Alcohol Breath Test	All Enrolled
	Listing 16.2.4.9	Glucose-6-Phosphate Dehydrogenase (G6PD)	All Enrolled
	Listing 16.2.4.10	Beck Depression Inventory (BDI)	All Enrolled
	Listing 16.2.4.11	Body Weight, Height and Body Mass Index (BMI)	All Enrolled
	Listing 16.2.4.12.1	Prior Medications	All Enrolled

	STATISTICAL ANALYSIS PLAN	QP17C19
		Page 47 of 53

	Listing Number	Listing Title	Population
	Listing 16.2.4.12.2	Concomitant Medications	All Enrolled
16.2.5 Compliance and Drug Concentration Data			
	Listing16.2.5.1	Malaria Inoculum Administration	All Enrolled
	Listing16.2.5.2	IMP Administration	All Enrolled
	Listing16.2.5.3	Rescue Medication Administration	All Enrolled
	Listing16.2.5.4	Blood Collection for PK Assessments, and measured OZ439 and PQP plasma concentrations	All Enrolled
	Listing16.2.5.5	Pharmacokinetic (PK) Parameters	PK
16.2.6 Individual Parasitaemia and Pharmacodynamic Data			
	Listing16.2.6.1	qPCR 18S Daily	All Enrolled
	Listing16.2.6.2	qRT-PCR pfs25 Daily	All Enrolled
	Listing16.2.6.3	qRT-PCR pfs25 Retrospective	All Enrolled
	Listing16.2.6.4	Pharmacodynamic (PD) endpoints (log ₁₀ PRR48, PCt1/2, subject recrudescence)	PD
16.2.7 Adverse Event Data			
	Listing16.2.7.1	All Adverse Events	All Enrolled
	Listing16.2.7.2	Serious Adverse Events	All Enrolled
	Listing16.2.7.3	Adverse Events of Special Interest (AESIs)	All Enrolled
	Listing16.2.7.4	Deaths	All Enrolled
16.2.8 Laboratory Data			
	Listing16.2.8.1.1	Individual Haematology Results	All Enrolled
	Listing16.2.8.1.2	Individual Abnormal Haematology Results	All Enrolled
	Listing16.2.8.2.1	Individual Biochemistry Results	All Enrolled
	Listing16.2.8.2.2	Individual Abnormal Biochemistry Results	All Enrolled
	Listing16.2.8.3.1	Individual Urinalysis Results (Dipstick)	All Enrolled
	Listing16.2.8.3.2	Individual Abnormal Urinalysis Results (Dipstick)	All Enrolled

	STATISTICAL ANALYSIS PLAN	QP17C19
		Page 48 of 53

	Listing Number	Listing Title	Population
	Listing16.2.8.4.1	Individual Urine Microscopy Results	All Enrolled
	Listing16.2.8.4.2	Individual Abnormal Urine Microscopy Results	All Enrolled
16.4 Other Safety Data			
	Listing16.4.1	Vital Signs	All Enrolled
	Listing16.4.2	Individual Abnormal Vital Signs	All Enrolled
	Listing16.4.3	ECG Parameters and Changes from Baseline	All Enrolled
	Listing16.4.4	Abnormal ECG Findings	All Enrolled
	Listing16.4.5	Physical Examination	All Enrolled
	Listing16.4.6	Malaria Clinical Score	All Enrolled
	Listing16.4.7	Additional Comments	All Enrolled

APPENDIX 2: PLANNED SUMMARY TABLES

The following tables are planned to be generated for the QP17C19 study (note: Numbering is indicative only and may be updated based on CSR requirements):

	Table Number	Table Title	Population
14.1 Demographic Data			
	Table14.1.1	Study Participation and Disposition	All Enrolled
	Table14.1.2	Demographics and Baseline Characteristics	All enrolled
	Table14.1.3	IMP Administration	All Enrolled
	Table14.1.4	Analysis Population	All Enrolled
14.2 Pharmacokinetic, Parasitaemia, and Pharmacodynamic Data			
	Table14.2.1	Summary of OZ439 and PQP concentrations in plasma by timepoint and by dose group	PK
	Table14.2.2	Summary of PK endpoints by dose group	PK
	Table14.2.3	Summary of qPCR 18S Daily measurements by timepoint and by dose group	PD
	Table14.2.4	Summary of PD endpoints by dose group	PD
	Table 14.2.5	Treatment comparison across dose groups based on QB test for between-treatment differences of weighted slope	PD
	Table14.2.6	Final PK parameter estimates	PK
	Table14.2.7	Final PD parameter estimates	PKPD
14.3 Safety Data			
	Table14.3.1.1a	Overall Summary of Inoculum-Emergent Adverse Events	Inoculum
	Table14.3.1.1b	Overall Summary of Treatment-Emergent Adverse Events	Safety
	Table14.3.1.2a	Inoculum-Emergent Adverse Events by MedDRA System Organ Class and Preferred Term	Inoculum

	STATISTICAL ANALYSIS PLAN	QP17C19
		Page 50 of 53

Table Number	Table Title	Population
Table 14.3.1.2b	Treatment-Emergent Adverse Events by MedDRA System Organ Class and Preferred Term	Safety
Table 14.3.1.3a	Inoculum-Related Inoculum-Emergent Adverse Events by MedDRA System Organ Class and Preferred Term	Inoculum
Table 14.3.1.3b	IMP-Related Treatment-Emergent Adverse Events by MedDRA System Organ Class and Preferred Term	Safety
Table 14.3.1.4a	Inoculum-Emergent Adverse Events by MedDRA System Organ Class, Preferred Term and Maximum Severity	Inoculum
Table 14.3.1.4b	Treatment-Emergent Adverse Events by MedDRA System Organ Class, Preferred Term and Maximum Severity	Safety
Table 14.3.1.5a	Overall Summary of Inoculum-Emergent AESIs	Inoculum
Table 14.3.1.5b	Overall Summary of Treatment-Emergent AESIs	Safety
Table 14.3.1.6a	Inoculum-Emergent Adverse Events by MedDRA Preferred Term	Inoculum
Table 14.3.1.6b	Treatment-Emergent Adverse Events by MedDRA Preferred Term	Safety
Table 14.3.2a	Malaria Clinical Score and Change from Baseline	Inoculum
Table 14.3.2b	Malaria Clinical Score and Change from Baseline	Safety
14.3.4 Clinical Laboratory Data		
Table 14.3.4.1a	Haematology Results and Change from Baseline (Inoculum)	Inoculum
Table 14.3.4.1b	Haematology Results and Change from Baseline (IMP)	Safety
Table 14.3.4.2a	Biochemistry Results and Change from Baseline (Inoculum)	Inoculum
Table 14.3.4.2b	Biochemistry Results and Change from Baseline (IMP)	Safety
Table 14.3.4.3a	Cross-Tabulation of Haematology Abnormalities Versus Baseline (Inoculum)	Inoculum

	STATISTICAL ANALYSIS PLAN	QP17C19
		Page 51 of 53

	Table Number	Table Title	Population
	Table14.3.4.3b	Cross-Tabulation of Haematology Abnormalities Versus Baseline (IMP)	Safety
	Table14.3.4.4a	Cross-Tabulation of Biochemistry Abnormalities Versus Baseline (Inoculum)	Inoculum
	Table14.3.4.4b	Cross-Tabulation of Biochemistry Abnormalities Versus Baseline (IMP)	Safety
14.3.5 Vital Signs			
	Table14.3.5.1a	Vital Signs Results and Change from Baseline (Inoculum)	Inoculum
	Table14.3.5.1b	Vital Signs Results and Change from Baseline (IMP)	Safety
	Table14.3.5.2a	Abnormal Vital Signs Results (Inoculum)	Inoculum
	Table14.3.5.2b	Abnormal Vital Signs Results (IMP)	Safety
14.3.6 ECG Findings			
	Table14.3.6.1a	ECG parameters and Change from Baseline (Inoculum)	Inoculum
	Table14.3.6.1b	ECG parameters and Change from Baseline (IMP)	Safety
	Table14.3.6.2a	Abnormal ECG Results (Inoculum)	Inoculum
	Table14.3.6.2b	Abnormal ECG Results (IMP)	Safety
	Table14.3.6.3a	ECG Clinical Assessment (Inoculum)	Inoculum
	Table14.3.6.3b	ECG Clinical Assessment (IMP)	Safety

APPENDIX 3: PLANNED SUMMARY FIGURES

The following figures are planned to be generated for the QP17C19 study (note: Numbering is indicative only and may be updated based on CSR requirements):

Figure Number	Figure Title	Population
